Study Design	Survey/Questionnaire and Behavioral Intervention		
Primary Objective	Adapt a cardiovascular disease risk assessment tool for use in adolescent and young adult clinical practices in Atlanta		
Secondary Objective(s)	 Use qualitative methods to elicit information about what adaptations are needed to make a cardiovascular disease risk assessment tool and a companion behavioral intervention appropriate with adolescents/young adults Adapt a cardiovascular disease risk assessment tool and companion behavioral intervention into a single integrated application for use in primary/reproductive care settings serving adolescent/young adult women Pilot the new cardiovascular disease risk assessment tool in primary/reproductive care settings serving adolescent/young adult women 		
Research	Mobile app (#HerHeart) development;		
Intervention(s)/Interactions	survey/questionnaire; audio-recorded interviews		
Study Population	Adolescent and young adult women presenting for care at the CHOA Hughes Spalding Adolescent Medicine clinic and the Grady Health System Teen Program		
Sample Size	60 adolescent/young adult women 10 health care providers		
Study Duration for individual participants	Phase 1: one hour Phase 2: six months Phase 3: three months		
Study Specific Abbreviations/ Definitions	AYA – adolescent and young adult CHOA – Children's Healthcare of Atlanta CVH – cardiovascular health CVD – cardiovascular disease HBM – Health Belief Model		
	HCP – health care providers HHS – Healthy Heart Score		

	VAS – Visual Analog Scale	
Funding Source (if any)	This study is being considered for funding by the NIH	
	National, Heart, Lung and Blood Institute.	

2. Objectives

The purpose of this study is adapt a Healthy Heart Score tool for use in adolescent and young adult (AYA) clinical practices in Atlanta. Our central hypothesis is that a developmentally appropriate lifestyle-based risk prediction tool, delivered during wellness, mental health, and reproductive health visits and reinforced through personalized goal setting, will be acceptable to young women and their providers and feasible to integrate into practice. The aims of the present study are as follows:

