Aim 1. Using qualitative methods, elicit information about what adaptations are needed to make the Healthy Heart Score risk assessment tool and a companion behavioral intervention appropriate for use with AYAs and HCPs. We will survey and interview 20 AYA women and 10 HCP in primary care wellness, mental health, and reproductive health practice settings.

Aim 2. Adapt the Healthy Heart Score risk assessment tool and a companion behavioral intervention into a single integrated application for use in primary/reproductive care settings serving AYA women. We will recruit 10 additional AYA to iteratively test the new application using user-centered design principles.

Aim 3. Evaluate the usability and initial feasibility of #HerHeart. We will recruit 60 additional AYA participants and the same 10 HCPs from Aim 1 to evaluate the usability and feasibility of the web tool.

3. Background

Cardiovascular disease (CVD) remains the number one killer of women in the US despite decades of progress in risk factor detection and treatment.¹ Awareness of CVD risk and risk factor control remain critical barriers to reversing this trend. In our study of young adults participating in the National Health and Nutrition Examination Survey 2011-2014, a substantial proportion of participants with hypercholesterolemia (43.1%), hypertension (37.3%) and diabetes (30%) at the time of their study exam reported no awareness of these diagnoses, and >75% of young adults with borderline levels of these risk factors were unaware of their risk.² This is highly concerning given the high proportion of young adults who will transition from borderline or intermediate cardiovascular health (CVH) to poor CVH as they reach middle age.¹ Furthermore, even intermediate CVH in adolescence and young adulthood is associated with subclinical markers of CVD later in life.³⁻⁶

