This project will advance the state of the science regarding CVD risk communication with adolescent and young adult women within primary and reproductive health care systems. Adolescents and young adults are infrequently screened for CVD risk factors during health care encounters,¹⁴ and many young people do not have a routine source of primary care.¹⁵ Grounded in the conceptual framework of the Health Belief Model (HBM),¹⁶ this feasibility study will incorporate CVD risk assessment into wellness, mental health, and reproductive health visits for adolescent and young adult women in two clinical practices that serve a primarily African American population with low socioeconomic status and high cardiovascular risk. We will address two key concepts of the Health Belief Model: a) targeting adolescent and young adult women's perceived susceptibility to CVD, and b) providing a cue to action to set personalized goals for improving their CVH as they transition to adulthood. We hypothesize that a lifestyle-based risk prediction tool (the Healthy Heart Score) coupled with a companion behavioral intervention can be adapted for use as an integrated application for young women.

4. Study Endpoints

Phase 1: Using qualitative methods, elicit information about necessary adaptations to the Healthy Heart Score risk assessment tool and a companion behavioral intervention. The primary endpoint of this portion of the study is the collection of survey and interview data from 20 AYA and 10 HCP.

Phase 2. Adapt the Healthy Heart Score (HHS) risk assessment tool and behavioral intervention frameworks into a single integrated application. The primary endpoint of this portion of the study is the creation of the single integrated application, #HerHeart.

Phase 3. Evaluate the usability and initial feasibility of #HerHeart. The primary endpoint of this portion of the study is the assessment of the usability of the tool and the feasibility of recruitment for a larger clinical trial.

5. Study Intervention / Design

This is a three-part study. In Aim 1/Phase 1, we will use qualitative data to understand necessary adaptations to two existing tools developed for adults. In Aim2/Phase 2, we will use user-centered design to make those adaptations in conjunction with participants. Aim 3/Phase 3 will test the usability of the developed tool and the feasibility of a larger clinical trial.

[figure not shown]

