Phase 2: We will employ an iterative user-centered design process to beta-test the integrated application with up to 10 additional AYA women. The additional AYA women will be recruited from the Emory Pipeline Collaborative (EPiC). Working with the Georgia CTSA Innovation Catalyst, we will engage in cycles of rapid prototyping, starting with a simple prototype that represents the integrated application on a storyboard and adapt the content based on user feedback. We will then work with the Georgia CTSA App Hatchery to program the web-based integrated application compatible with mobile devices equipped with Android or iOS operation systems. Finally, we will engage AYA participants in live prototyping, presenting them with a functional prototype to react to as they complete the assessment tool in real-time.

Throughout the design process, we will conduct observational field tests by gathering information about how AYA participants use the application in real-time. We will elicit their feedback on the usability and desirability of the integrated application throughout the process, and adjust the application based on their feedback. We will also examine automatically generated data from the application itself to identify patterns of activity and common problems. The end-product of Aim 2 will be the final integrated application consisting of a lifestyle-based CVD risk assessment and companion behavioral intervention. For the remainder of the protocol, we will refer to the integrated application as #HerHEART; however, the application will formally be named with input from participants in Aim 1.

			Aim 3 Measures - HCP	
Primary Outcomes (3- month Time Frame) Changes in overall #HerHeart risk score Changes in overall composite of diet Changes in full and vegetable intake Changes in read and processed meats intake Changes in sugar and sweetened beverages Changes in nut consumption Changes in nut consumption Changes in alcohol consumption Changes in alcohol consumption	in SBP • Changes in DBP	Exploratory Outcomes WAMMI for #HerHeart WAMMI for Healthy Heart Score Likelihood of recommending #HerHeart to friends (0-10) Likelihood of behavior change (0-10) VAS Eating Disorder Diagnostic Scale (EDDS) # of participants approached # who agreed to participate Completion/dropou rate	 Likelihood of incorporating #HerHeart into practice (0-10) 	

Phase 3: We will recruit 60 additional AYA

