Primary outcomes will include changes in overall #HerHeart risk score, composite dietary score, fruit and vegetable intake, red/processed meats intake, soda and sweetened beverages intake, nut consumption, cereal fiber consumption, alcohol consumption, nicotine use, and physical activity over a 3-month period. Secondary outcomes will include changes in BMI and systolic and diastolic blood pressure over a 3-month period. Exploratory outcomes will include usability of the HerHeart tool and Healthy Heart Score as assessed by the WAMMI, adolescents' likelihood of recommending the tool to friend, adolescents' self-reported likelihood of behavior change, adolescents' understanding of heart disease risk as measured by VAS, change in EDDS score, number of participants approached and participated, completion/dropout rate, HCP rated usefulness of HerHeart tool to the practice, and HCP rated likelihood of

incorporating HerHeart tool into practice.

All phases: The probability and magnitude of risks will be minimized by conducting study procedures in private settings, collecting data in REDCap, a secure web-based application designed exclusively to support data capture for research studies, and collaborating with the Georgia CTSA to ensure data security of the mobile app.

6. Data and Specimen Banking

Data from surveys/questionnaires, audio recordings, and interviews will be stored until the completion of data analysis and manuscript publication. Only approved study personnel listed on the protocol will have access to the data.

7. Sharing of Results with Participants

Personal Healthy Heart Score risk assessments will be shared with participants at each stage of the study. Participants will be encouraged to share their results with their primary care physicians, but results will not be directly shared with others.

8. Study Timelines

Individuals in Aim 1/Phase 1 will participate for ~one hour, one time. Individuals in Aim 2/Phase 2 will participate for up to two hours for each design session which will occur over 6 months. Aim 3/phase 3 will occur over 3 months. The total duration of the overall study is 15 months, which includes subject participation and data analysis.

9. Subject Population

Subjects will be recruited from the CHOA Hughes Spalding Adolescent Medicine Clinic and the Grady Teen Health Program. The following inclusion/exclusion criteria will be used for subject recruitment:

Inclusion Criteria (AYAs):

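### Section 4 and the Section 5 outcome list name different primary endpoints for Phase 3, and nothing says which governs

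*Combined protocol and SAP*

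**What the plan says.** Section 4 (Study Endpoints), on Phase 3: "The primary endpoint of this portion of the study is the assessment of the usability of the tool and the feasibility of recruitment" for a later, larger trial.

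Two other places point the same way in general terms. Section 2 has "Aim 3. Evaluate the usability and initial feasibility of #HerHeart", and the opening paragraph of Section 5 has "Aim 3/Phase 3 will test the usability of the developed tool and the feasibility of a larger clinical trial".

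The Phase 3 outcome list later in Section 5 sets three tiers:

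- **Primary:** "Primary outcomes will include changes in overall #HerHeart risk score, composite dietary score, fruit and vegetable intake", and seven more 3-month changes.
- **Secondary:** "Secondary outcomes will include changes in BMI and systolic and diastolic blood pressure over a 3-month period".
- **Exploratory:** "Exploratory outcomes will include usability of the HerHeart tool and Healthy Heart Score as assessed by the WAMMI", together with the numbers approached and participating, completion or dropout, EDDS and VAS, and the provider (HCP) ratings of usefulness and likely uptake.

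The Aim 3 measures table uses the same tiers; one of its columns begins "Exploratory Outcomes WAMMI for #HerHeart".

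The Phase 3 analysis paragraph in Section 5 gives two numeric success rules: more than 80% of adolescent and young adult (AYA) participants and HCPs rating the tool above average on the WAMMI, and an HCP acceptability mean of 8 out of 10. Its only named tests are paired t-tests for EDDS and VAS. Section 16 adds that all data will be descriptive.

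**The concern.** A protocol should identify one primary result for each phase before the data are seen. Here two current passages identify different ones, and what one calls primary the other puts in its lowest tier. A report could lead with usability and recruitment, or with a change in risk score or diet, and cite the protocol either way. The usability rule could fail while one of ten changes looks favourable, or the reverse.

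The two results also differ in kind. Usability is rated by every AYA participant who completes the tool at the first visit, and by the HCPs. The 3-month changes come only from AYA participants who accept an optional intervention phase and return for the final visit, a number the plan does not give. No comparator is described, so a before-after change in that group cannot be attributed to the tool.

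**Working it through.** The plan gives no alpha, power or effect size for Phase 3, so there is no figure to reproduce. The check is a comparison of text and a count.

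**Step 1: count the Section 5 tiers.** The prose list of primary changes is: (1) #HerHeart risk score, (2) dietary composite, (3) fruit and vegetables, (4) red or processed meat, (5) sweetened drinks, (6) nuts, (7) cereal fiber, (8) alcohol, (9) nicotine, (10) physical activity. The secondary changes are BMI, systolic and diastolic blood pressure. So 10 + 3 = 13 changes rank above the exploratory tier. The count uses the prose, which is intact. The extracted Aim 3 table is damaged; it supports the tiers but not the count.

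**Step 2: set the rankings side by side.**

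| Item | Section 4 | Section 5 outcome list |
|---|---|---|
| Usability of #HerHeart | Primary | Exploratory |
| Feasibility of recruitment | Primary | Exploratory (numbers approached and participating) |
| Ten risk-score and behavior changes | Not mentioned | Primary |
| BMI and blood pressure changes | Not mentioned | Secondary |

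None of the ten primary changes measures usability or recruitment, so the two primary sets do not overlap.

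**Step 3: look for a statement of precedence.** None appears in Sections 2, 4, 5 or 16. Section 16 describes how data will be handled but does not rank outcomes.

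**Step 4: see where the analysis rules attach.** The WAMMI threshold, the HCP mean of 8 and the paired t-tests all concern outcomes that Section 5 calls exploratory. The ten primary changes have no specific analysis, only the general statement in Section 16. The analysis paragraph therefore fits Section 4 better than it fits the list that follows it.

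**Step 5: check whether the usability rule is usable as a primary criterion.** It does not say whether AYA and HCPs are judged together or separately. If all 60 AYA and all 10 HCPs give ratings:

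- AYA alone: 0.80 × 60 = 48, so at least 49 are needed.
- HCPs alone: 0.80 × 10 = 8, so at least 9 are needed.
- Together: 0.80 × 70 = 56, so at least 57 are needed.

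With 49 AYA and 8 HCPs favourable, 57/70 = 81.4% passes jointly, while 8/10 = 80% does not exceed 80% for HCPs alone. The reading can decide the result.

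**The case against.** The strongest reply is that little depends on the labels. The study-level primary objective is to adapt the tool, Section 16 calls all data descriptive, and no sample-size argument rests on either list. The Aim 3 table also heads its primary tier with a 3-month time frame, which suggests that tier was meant for the optional intervention phase only.

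Part of this stands. It limits the consequence to how results are presented. It does not remove the conflict: a descriptive report still has a lead result, and the same table ranks WAMMI usability as exploratory. Nor does a distinction between endpoint and outcome help, since both passages use the word primary for the same phase.

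Three stronger readings are tempting but not supported:

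- A reader might infer that the whole protocol, apart from one list, makes recruitment primary. Only Section 4 names recruitment. Aim 3 refers to the feasibility of the tool, and the opening of Section 5 to that of a larger trial. The central hypothesis is that the tool "will be acceptable to young women and their providers and feasible to integrate into practice", which names neither usability nor recruitment.
- A reader might infer an inflated false-positive rate from ten primary outcomes. No test or significance level is set for them, so there is no error rate to inflate.
- A reader might infer that the recruitment target is itself contradictory, because Section 22 seeks 60 AYA in a year and Section 11 gives 90. The 90 is the sum over the aims (20 + 10 + 60), and the Aim 3 window of months 12 to 24 is about a year.

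**Conclusion.** The point holds: this is an internal contradiction in current, intact text, and the plan is wrong as written. Section 4 and the Section 5 outcome list give non-overlapping primary sets for Phase 3, with 13 three-month changes ranked above the two components of the Section 4 endpoint. The harm is the freedom to choose the headline after seeing the data, including a change without a comparator in participants who opted in and returned. It does not extend to the study's main objective of adapting the tool, or to any stated power or error rate.

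The conclusion rests on the design being single-group. The documents do not use that term, but they describe no comparator and offer the intervention phase to AYA participants generally.

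**What to change.** Before analysis, reconcile Section 4, the Section 5 outcome list and the Aim 3 table to one hierarchy. The option that fits Section 4 and Aim 3 is:

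1. **Primary:** WAMMI usability of #HerHeart under the existing >80% rule, stating whether AYA and HCPs are judged together or separately; and recruitment, as number agreeing divided by number approached. Report each with an exact 95% confidence interval.
2. **HCP acceptability (mean of 8):** assign an explicit tier. It is the other stated success rule and relates to the providers' part of the central hypothesis.
3. **All 13 three-month changes:** place below the primary. Report each as mean paired change with 95% confidence interval and number analysed, and state that no efficacy conclusion will be drawn.

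If the investigator prefers the Section 5 tiers, Section 4 must be changed to match.

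The cost is an amendment to wording, with no added participants or measurements. Under the option above, the behavior, BMI and blood pressure changes can no longer be headlined. The document (version 7.0.1, 10/28/2022) does not say whether Phase 3 data collection had begun; if it had, the change should be dated and justified.

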Figure 2. Timeline for the proposed study: Aim 1: months 0-6, Aim 2: months 7-12; Aim 3: months 12-24

Procedures Involved

Phase 1: AYA participants (n=20) will complete a brief initial survey on a tablet to collect data listed in Table 1. Participants will also complete the Visual Analog Scale (VAS) to allow them to estimate their perceived 10-year risk of CVD, lifetime risk of CVD, and perceived severity of CVD. Additionally, participants will complete the Healthy Heart Score (HHS) beta version and answer questions following a semi-structured interview guide to elicit thoughts and comments about the app (AYA Data Collection.pdf). Participants

Aim 1 Measures – AYA	Aim 1 Measures - HCP		
i. Brief Initial Survey	v. Provider Survey		
Age Race/ethnicity Mother's highest level of education Zip code VAS AHA Women's Health Survey ii. Structured Observation Tool (time stamps)	Age Gender Race/ethnicity Degree Practice Site Years in Practice V. Provider Semi-Structured Interview: HHS/DPP		
Health Belief Model domains Length of time to complete tool Optimal location to complete tool Understanding of questions Suggested adaptations iv. Semi-Structured Interview re: DPP modules Optimal delivery modality Preferred frequency/timing of messages Understanding of content Necessary adaptations	Current Provision of CVD prevention care Comfort with CVD risk assessment Barriers/facilitators to providing CVD care Perceived relevance of HHS/DPP Practicality of using CVD application in practice		

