women and the same 10 HCPs from Aim 1 to evaluate the #HerHeart tool's usability and feasibility. AYA participants will complete a brief initial survey consisting of demographic information and the Visual Analog Scale (VAS) and the #HerHeart tool in clinic. AYA participants will the rate the usability of the #HerHeart tool using the Website Analysis and Measurement Inventory (WAMMI), the likelihood they would recommend the app to their friends, and the likelihood of behavior change. AYA participants will then be offered the opportunity to continue into the 3-month intervention phase. We will document the reasons for declining as part of tracking feasibility. At the beginning of the intervention phase, participants will complete the Eating Disorder Diagnostic Scale (EDDS). Participants will then be texted 1 month and 2-months post-enrollment reminding them of any goals/areas of improvement indicated by their end assessment in the #HerHeart Tool. Three months post-enrollment, participants will attend the final study visit in the phlebotomy room on the second floor of CHOA Hughes Spalding. In this visit, AYA participants height, weight and blood pressure will be measured. Participants will also be asked to complete the #HerHeart tool again and the same online study scales collected at baseline (EDDS and VAS). They will also be asked to complete the Harvard Healthy Heart Score and evaluate the usability using the WAMMI. HCP participants will complete a survey consisting primarily of demographic information and the #HerHeart tool. HCP participants will then rate the usability of the tool using the WAMMI, the usefulness of the #HerHeart to their practice and the likelihood they would incorporate it into usual clinical care.

Data analysis will consist of descriptive statistics for the WAMMI and Likert scale surveys. Usability will be defined as >80% of AYA and HCP rating the application as above average on the WAMMI. Acceptability to HCP will be defined as a mean of 8 out of 10 Likert Scale items. Paired t-tests will be used to compare the baseline and 3-month data for the continuous scales (EDDS, VAS).

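### The VAS outcome is named understanding of heart disease risk, but the planned paired t-test shows only whether average perceived risk or severity shifted

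*Combined protocol and SAP*

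**What the plan says.** All of this is in section 5 (Study Intervention / Design) unless stated otherwise.

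- **Outcome.** The exploratory list, which opens "Exploratory outcomes will include usability of the HerHeart tool and Healthy Heart Score as assessed by the WAMMI", includes adolescents' "understanding of heart disease risk as measured by VAS". The Aim 3 measures table says only VAS.
- **Content of the scale.** Under Phase 1, participants complete the VAS "to allow them to estimate their perceived 10-year risk of CVD, lifetime risk of CVD, and perceived severity of CVD". Phase 3 uses a scale of the same name and does not redefine it.
- **Analysis.** "Paired t-tests will be used to compare the baseline and 3-month data for the continuous scales (EDDS, VAS"). No direction of change is said to mean better understanding, and no success criterion is set for the VAS.
- **Available comparator.** The #HerHeart tool is completed at baseline, and at month 3 "Participants will also be asked to complete the #HerHeart tool again". No comparison of the VAS with the tool's result is planned. The AHA Women's Health Survey appears only among the Aim 1 measures.
- **Feedback.** Section 7 states: "Personal Healthy Heart Score risk assessments will be shared with participants at each stage of the study".
- **Order.** At baseline the VAS is listed before the tool. At month 3 the tool is listed before the repeated scales.
- **Target concept.** Section 3 names perceived susceptibility, from the Health Belief Model, as one of two concepts to be addressed.

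**The concern.** Perceived risk is a belief. Understanding, in any useful sense, concerns how that belief relates to the participant's actual result. Participants are told their own result, so a well-informed change may be upward for one and downward for another. A mean change ignores who moved in which direction and why.

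Two misreadings follow. A report could claim improved understanding because everyone's perceived risk rose, whatever her result. Or it could report no change in understanding when over- and under-estimators had both corrected themselves. Perceived severity adds a further difficulty: the tool calculates risk, so that item has no calculated value to be compared with.

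**Working it through.** The documents give no SD, effect size, alpha or sample size for the VAS, so there is no planned figure to reproduce. The check uses one exact example and then a power calculation on assumed inputs.

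**1. Exact example (no distribution assumed).** Take 60 participants, the Phase 3 enrolment, each with a calculated risk of 30. Half move from 60 to 40 and half from 0 to 20.
- Mean VAS change = (−20 + 20)/2 = 0.
- Mean absolute error before = (30 + 30)/2 = 30; after = (10 + 10)/2 = 10.

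Every participant is closer to her own figure, and the mean change is zero.

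**2. Everyone moves halfway to her own score.** Assumed inputs: n = 40 (the number entering the 3-month phase is not stated); score mean 40, SD 15, unchanged between visits; baseline VAS mean m, SD 15, unrelated to the score; follow-up noise SD 10; two-sided 5% test.
- Change d = 0.5 × (score − VAS) + noise.
- SD of d = √(0.25 × (225 + 225) + 100) = √212.5 = 14.58.
- Standard error = 14.58/√40 = 2.305.
- Noncentrality = 0.5 × (40 − m)/2.305, with power from the noncentral t on 39 degrees of freedom.

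| Baseline VAS mean m | Mean change | Noncentrality | Probability of rejection |
|---|---|---|---|
| 40 | 0 | 0 | 5% |
| 35 | 2.5 | 1.08 | 18% |
| 30 | 5.0 | 2.17 | 56% |
| 25 | 7.5 | 3.25 | 89% |
| 20 | 10.0 | 4.34 | 99% |

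Simulations of 4,000 trials agree, apart from a spread of 55% to 58% at m = 30. In every row the link to personal risk improves equally. The correlation of follow-up VAS with score is 112.5/(15 × 14.58) = 0.51. On the Spearman scale the simulated mean rises from 0.00 to about 0.48. The t-test result therefore depends on the average starting error, not on how much participants learned.

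**3. Everyone rises by 8, whatever her score.** Mean change is 8, SD 10, and noncentrality = 8/(10/√40) = 5.06. Rejection is 99.8%, and the VAS–score correlation stays at 0.

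**4. What a rank correlation misses.** Let baseline VAS average 20 against a score mean of 40, with correlation 0.5, and let everyone rise by 8 with noise SD 10.
- Error (VAS − score) before: mean −20, SD √(225 + 225 − 225) = 15. After: mean −12, SD √(325 + 225 − 225) = 18.03.
- Mean absolute error (folded normal) falls from 21.3 to 17.5, about 3.8 points.
- The correlation falls from 0.50 to 0.5 × 15/√325 = 0.42; simulated Spearman falls from 0.47 to 0.39.

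Estimates become more accurate while the rank correlation falls.

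**5. Precision of a correlation.** By a rough Fisher approximation at n = 40, a coefficient of 0.48 has z = 0.523 ± 1.96/√37, or 0.201 to 0.845. That is a 95% interval of about 0.20 to 0.69.

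**The case against.** The best case for the plan is that this is one loose word. The measures table says VAS, the scale's content is stated plainly, and no decision rule is attached. The named theoretical target is perceived susceptibility, for which a mean change is a proper summary. All of that stands. It confines the point to what may be concluded from the result; it does not make the label right.

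A reader might infer that the planned test would usually miss real learning. The documents do not support that. The 5% figure needs over- and under-estimates to balance exactly. The background in section 3 points towards under-estimation: more than 75% of young adults with borderline risk factors were unaware of their risk, and 90% of young women were unaware that CVD is the leading cause of death in women. These are not VAS data, but they make full cancellation a worst case.

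A reader might also infer that a uniform rise shows no gain in understanding, or that a Spearman correlation measures understanding properly. Neither holds. With a shared under-estimate, a uniform rise brings estimates closer to the truth, and the correlation does not register it (step 4). Absolute error would capture calibration, but it needs the VAS and the tool to share a scale, risk definition and time horizon, which the documents do not establish.

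Finally, section 16 calls all data descriptive only, which conflicts with the t-tests in section 5. The two need reconciling, but a descriptive mean change has the same limit.

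**Conclusion.** The concern holds as a mismatch between the outcome's name and its analysis. The paired result can support a statement about average perceived risk and severity; by itself it cannot support one about understanding. The exact example shows this without any distributional assumption. The rejection rates (5% to 99% when everyone learns equally, over 99% for a uniform rise of 8) rest on the assumed means, SDs, noise and n = 40. They show the range of behaviour and do not predict this trial's result.

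The importance is low. The outcome is exploratory, in a usability and feasibility study, and the documents do not make any primary or secondary conclusion depend on it.

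**What to change.** 1. Rename the paired VAS result *change in perceived risk and perceived severity*, tie it to the susceptibility concept in section 3, and state that no conclusion about understanding will be drawn from it alone.
2. As a descriptive exploratory addition, show change in the two VAS risk items (10-year and lifetime, not severity) by third of the baseline #HerHeart score. Give the Spearman correlation of each item with the #HerHeart score at baseline and at month 3, with 95% confidence intervals.
3. State that the correlation shows whether perceived risk ranks with calculated risk. It does not show calibration and cannot detect correction of a shared under- or over-estimate.
4. Specify that the VAS is given before the tool at month 3, as it is listed at baseline, so that answers do not echo a score just shown.

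The cost is a change of wording, a small extra analysis of data already collected (with wide intervals at this sample size), and a fixed questionnaire order at the month-3 visit.
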